Appendix B: Toxicity Table

Local Reactogenicity Grading

Local Reaction to Injectable Product	Mild (Grade 1)	Moderate (Grade 2)	Severe (Grade 3)	Potentially Life Threatening (Grade 4)
Pain/Tenderness/Pruritus	Does not interfere with activity	Repeated use of non-narcotic pain reliever > 24 hours or interferes with activity	Any use of narcotic pain reliever or prevents daily activity	Emergency room (ER) visit or hospitalization
Erythema/Redness/Bruising ¹	2.5 – 5 cm	5.1 – 10 cm	> 10 cm	Necrosis or exfoliative dermatitis
Induration/Swelling ²	2.5 – 5 cm and does not interfere with activity	5.1 – 10 cm or interferes with activity	> 10 cm or prevents daily activity	Necrosis

¹ In addition to grading the measured local reaction at the greatest single diameter, the measurement should be recorded as a continuous variable.

² Induration/Swelling should be evaluated and graded using the functional scale as well as the actual measurement.

Vital Sign AE Grading

Vital Signs ¹	Mild (Grade 1)	Moderate (Grade 2)	Severe (Grade 3)	Potentially Life Threatening (Grade 4)
Fever ² (°C) (°F)	38.0 – 38.4 100.4 – 101.1	38.5 – 38.9 101.2 – 102.0	39.0 – 40 102.1 – 104	> 40 > 104
Tachycardia - bpm	101 – 115	116 – 130	> 130	ER visit or hospitalization for arrhythmia
Bradycardia - bpm ³	50 – 54	45 – 49	< 45	ER visit or hospitalization for arrhythmia
Hypertension (systolic) - mm Hg	141 – 150	151 – 155	> 155	ER visit or hospitalization for malignant hypertension
Hypertension (diastolic) - mm Hg	91 – 95	96 – 100	> 100	ER visit or hospitalization for malignant hypertension
Hypotension (systolic) – mm Hg	85 – 89	80 – 84	< 80	ER visit or hospitalization for hypotensive shock

¹ Subject should be at rest for all vital sign measurements.

² Oral temperature; no recent hot or cold beverages or smoking.

³ When resting heart rate is between 60 – 100 beats per minute. Use clinical judgment when characterizing bradycardia among some healthy subject populations, for example, conditioned athletes.

Systemic AE Grading

Systemic adverse events ¹	Mild (Grade 1)	Moderate (Grade 2)	Severe (Grade 3)	Potentially Life Threatening (Grade 4)
Feverish	No interference with activity	Some interference with activity not requiring medical intervention or use of 1-2 doses of antipyretics	Prevents daily activity or use of >2 doses of antipyretics in 24 hours	ER visit or hospitalization
Chills/Rigors	No interference with activity or 1 – 2 episodes/24 hours	Some interference with activity or > 2 episodes/24 hours	Prevents daily activity	ER visit or hospitalization for hypotensive shock
Sweats	No interference with activity	Some interference with activity not requiring medical intervention	Prevents daily activity	ER visit or hospitalization
Diarrhea	2 – 3 loose stools or < 400 gms/24 hours	4 – 5 stools or 400 – 800 gms/24 hours	6 or more watery stools or > 800gms/24 hours or requires outpatient IV hydration	ER visit or hospitalization
Headache	No interference with activity	Repeated use of non-narcotic pain reliever > 24 hours or some interference with activity	Significant; any use of narcotic pain reliever or prevents daily activity	ER visit or hospitalization
Fatigue/ Malaise	No interference with activity	Some interference with activity not requiring medical intervention	Prevents daily activity	ER visit or hospitalization
Back Pain	No interference with activity	Some interference with activity; use of 1-2 doses of medication	Prevents daily activity	ER visit or hospitalization
Chest Pain (non-musculoskeletal)	Transient (< 24 hours) or intermittent chest pain with no or minimal interference	Persistent chest pain resulting in greater than minimal interference with usual activities	Persistent chest pain resulting in inability to perform usual activities secondary to chest pain	ER visit or hospitalization
Myalgia	No interference with activity	Repeated use of non-narcotic pain reliever > 24 hours or some interference with activity	Any use of narcotic pain reliever or prevents daily activity	ER visit or hospitalization

Systemic adverse events ¹	Mild (Grade 1)	Moderate (Grade 2)	Severe (Grade 3)	Potentially Life Threatening (Grade 4)
Arthralgia	No interference with activity	Repeated use of non-narcotic pain reliever > 24 hours or some interference with activity	Any use of narcotic pain reliever or prevents daily activity	ER visit or hospitalization
Nausea/Vomiting	No interference with activity or 1 – 2 episodes/24 hours	Some interference with activity or > 2 episodes/24 hours	Prevents daily activity, requires outpatient IV hydration	ER visit or hospitalization for hypotensive shock
Abdominal Pain	No interference with activity	Repeated use of non-narcotic pain reliever > 24 hours or some interference with activity	Any use of narcotic pain reliever or prevents daily activity	ER visit or hospitalization
Urticaria/Rash	No interference with activity	Requiring PO or topical treatment > 24 hours or IV medications or steroids for ≤24 hours	Requiring IV medication or steroids for >24 hours	ER visit or hospitalization
Edema	No interference with activity	Some interference with activity not requiring medical intervention	Prevents daily activity	ER visit or hospitalization
Pruritus	No interference with activity	Requiring PO or topical treatment > 24 hours or IV medications or steroids for ≤24 hours	Requiring IV medication or steroids for >24 hours	ER visit or hospitalization

¹ For other symptoms not listed, they should be graded as outlined in **Section 11.3.1**

***Adapted from Guidance for Industry: Toxicity Grading Scale for Healthy Adult and Adolescent Volunteers Enrolled in Preventative Vaccine clinical Trials.

Mali Laboratory AE Grading Hematology/Chemistry

Hematology and Biochemistry values ^{1, 2}	Mild (Grade 1)	Moderate (Grade 2)	Severe (Grade 3)	Potentially Life Threatening (Grade 4)
Hemoglobin (Male) - gm/dL	9.5 – 10.3	8.0 – 9.4	6.5 – 7.9	< 6.5 and / or requiring transfusion
Hemoglobin (Female) gm/dL	8.0 – 9.0	7.0 – 7.9	6.0 – 6.9	< 6 and /or requiring transfusion
WBC Increase – 10 ³ /μL	11.5 – 15.0	15.1 – 20.0	20.1 – 25.0	> 25.0
WBC Decrease - 10 ³ /μL	2.5 – 3.3	1.5 – 2.4	1.0 – 1.4	< 1.0 with fever
Granulocyte or Neutrophil Decrease - 10 ³ /μL	0.8 – 1.0	0.5 – 0.7	< 0.5	< 0.5 with fever
Platelets Decreased – 10 ³ /μL	100 – 110	70 – 99	25 – 69	< 25
Creatinine (Male) μmol/L	124.00 – 150.99	151.00 – 176.99	177.00 – 221.00	> 221.00 and requires dialysis
Creatinine (Female) μmol/L	107.00 – 132.99	133.00 – 159.99	160.00 – 215.99	> 216.00 and requires dialysis
Liver Function Tests –ALT U/L	75.0 – 150.9	151.0 – 300.9	301.0 – 600.0	> 600.0

¹The laboratory values provided in the tables serve as guidelines and are dependent upon institutional normal parameters. Institutional normal reference ranges should be provided to demonstrate that they are appropriate.

²The clinical signs or symptoms associated with laboratory abnormalities might result in characterization of the laboratory abnormalities as Potentially Life Threatening (Grade 4). For example, a low sodium value that falls within a grade 3 parameter should be recorded as a grade 4 hyponatremia event if the subject had a new seizure associated with the low sodium value.

Mali Adult Normals Chemistry

Serum ¹	Reference Range
Creatinine (Female) - μmol/L	< 72
Creatinine (Male) - μmol/L	48 – 98
ALT – U/L	< 41

¹The laboratory values provided in the table are based on Bancoumana, Malian adults (age 18-45 years old)

Hematology

Hematology¹	Reference Range
Hemoglobin (Female) - gm/dL	9.1 – 13.8
Hemoglobin (Male) - gm/dL	10.8 – 15.8
WBC – 10 ³ /μL	3.6 – 9.0
Absolute Granulocyte or Neutrophil Count - 10 ³ /μL	1.3 – 4.4
Absolute Lymphocyte Count - 10 ³ /μL	1.3 – 4.4
Platelet Count (Female)- 10 ³ /μL	144 – 413
Platelet Count (Male)- 10 ³ /μL	114 – 335

¹The laboratory values provided in the table are based on Bancoumana, Malian adults (age 18-45 years old)

Urine Dip/Urinalysis

Urine¹	Reference Ranges
Protein	None
Blood (microscopic) – red blood cells per high power field (RBC/HPF)	None or Trace < 1

¹The laboratory values provided in the table are based on Bancoumana, Malian adults (age 18-45 years old)

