11.3 Investigator Assessment of Adverse Events

If a diagnosis is clinically evident (or subsequently determined), the diagnosis rather than the individual signs and symptoms or lab abnormalities will be recorded as the AE.

All solicited (see **Table 6** below) and unsolicited AEs will be recorded through Day 7 after each injection. Injection site reactions will be assessed until Day 7 after injection (PfSPZ Vaccine or normal saline) or until resolved.

After the periods specified above only unsolicited AEs, SAEs, UPs, and NOCIs will be recorded.

Table 6: Solicited Adverse Events

Laboratory adverse events¹	
Hemoglobin (decreased hemoglobin)	Platelet count (thrombocytopenia or thrombocytosis)
WBC (leukopenia or leukocytosis)	Creatinine (Cr) (increased Cr)
ANC (neutrophil count decreased) or AGC (granulocyte count decreased)	ALT (increased ALT)
Local reactogenicity (secondary to PfSPZ Vaccine/normal saline) – through Day 7 post injection	
Injection site pain/tenderness	Injection site induration
Injection site erythema/redness	Injection site swelling/edema
Injection site pruritus	Injection site bruising
Systemic reactogenicity (secondary to PfSPZ Vaccine/normal saline) – through Day 7 post injection	
Rash	Urticaria
Generalized pruritus	Generalized Edema
Headache	Fever or feverish
Chills	Malaise/Fatigue
Myalgia	Arthralgia
Sweats	Diarrhea
Back Pain	Chest Pain (non-musculoskeletal)
Nausea/Vomiting	Abdominal Pain

¹ Note absolute lymphocyte counts will be capture on CRFs for use for research assessments. If clinically significant changes as determined by PI, these may also be reported as AEs as noted below.

Any laboratory abnormalities (other than those specified as safety labs in the protocol as defined by the values in the toxicity table) should be reported as AEs if they require intervention. Interventions include, but are not limited to, discontinuation of treatment, dose reduction/delay, additional assessments, or concomitant treatment. In addition, any medically important laboratory abnormality may be reported as an adverse event at the discretion of the investigator. This could include a laboratory result for which there is no intervention, but the abnormal value suggests a disease or organ toxicity. In addition, similar to solicited AEs, all laboratory AEs as defined in **Appendix C**, will be collected and graded for severity through 7 days after each vaccination until resolved.

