11.11 Pausing Criteria for a Subject

The decision to suspend administration of the study agent(s) for a single subject or for all subjects in a specific group requires discontinuation of use of the study agent to any study subject(s) until a decision is made whether or not to continue study agent in the study.

The pausing criteria for a single subject or for the subjects in this study include:

- A subject experiences an SAE or ≥ 2 or more Grade 3 or greater AE (excluding laboratory assays) that is unexpected (as determined by the IND sponsor) and is possibly, probably, or definitely related to the study agent;
OR
- Any safety issue that the Site Investigator determines should pause administration of the study agent to a single subject.

The IND sponsor, in collaboration with the PI, may also pause for an individual subject if a safety concern is identified during routine aggregate data analysis.

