11.13 Withdrawal of an Individual Subject

A subject will not be considered to have completed the trial if any of the following reasons apply:

1. *Research terminated by Sponsor or Investigator* – applies to the situation where the entire study is terminated by the sponsor or investigator, or other regulatory authority for any reason.
2. *Withdrawal of consent* – applies to a subject who withdraws consent to participate in the study for any reason.
3. *Noncompliant with protocol* – applies to a subject who does not comply with protocol-specific visits or evaluations, on a consistent basis, such that adequate follow-up is not possible, and the subject's safety would be compromised by continuing in the trial. This also applies to a subject who is lost to follow-up and is not reachable by telephone or other means of communication and cannot be located.
4. *Completed follow up after developing an AE* – applies to a subject who is withdrawn from study due to an AE, serious or otherwise. Any grade 3 or greater AE that is assessed as possibly, probably, or definitely related to vaccination, PfSPZ Vaccine or placebo (other than local reactions lasting <72 hours, or systemic reactions lasting <48 hours) will result in withdrawal of the subject from further vaccinations. Subjects may also be withdrawn for any AE that would cause continued participation in the study to not be in the best interest of the subject, as per the investigator's judgment. Any subject who will not receive any further vaccination because of an AE related to study agent will be followed for safety until at least resolution of that AE and will be encouraged to remain in the safety evaluation for the duration of the study.
5. *Other* – is used when previous categories do not apply and a written explanation is required.

If a subject withdraws or is withdrawn prior to completion of the study, the reason for this decision will be recorded in the source documents and CRFs. Any subject who has received at least one dose of vaccine will be encouraged to remain in the safety evaluation for the duration of the study. The subject's data will be included in the safety and immunogenicity analysis. If a subject fails to complete all planned vaccinations because of an AE or SAE, the subject will be followed until resolution or stabilization of the event. If a subject withdraws, the investigator will make a reasonable effort to determine the reason.

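### Three Appendix B laboratory rows (WBC decrease, male and female creatinine) leave values beyond Grade 3 ungraded, so a worse result can miss the stop that a milder one triggers

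*Combined protocol and SAP*

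**What the plan says.** Appendix B (Toxicity Table, Mali laboratory grading) prints these rows:

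- WBC decrease (10³/µL): Grade 3 is 1.0–1.4; Grade 4 is "< 1.0 with fever".
- Creatinine, male (µmol/L): Grade 3 is 177.00–221.00; Grade 4 is "> 221.00 and requires dialysis".
- Creatinine, female (µmol/L): Grade 3 is 160.00–215.99; Grade 4 is "> 216.00 and requires dialysis".

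Other rows of the same table are built differently. Neutrophil Grade 4 is "< 0.5 with fever", but neutrophil Grade 3 is any value below 0.5. Male haemoglobin Grade 4 is "< 6.5 and / or requiring transfusion", so the value alone is enough; the female row works the same way. Platelets, ALT and WBC increase have unconditional Grade 4 limits.

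The grades are used in three places:

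- Section 11.3: laboratory AEs "will be collected and graded for severity through 7 days after each vaccination until resolved".
- Section 11.13, item 4: apart from short-lived local and systemic reactions, a related AE of Grade 3 or greater "will result in withdrawal of the subject from further vaccinations". Laboratory AEs are not excluded.
- Section 11.10, criterion 4: the study pauses if 30% of an arm has the same laboratory abnormality at Grade 2 or higher.

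The subject-level pausing rule in Section 11.11 does exclude laboratory results. Apart from SAEs, it acts on a "Grade 3 or greater AE (excluding laboratory assays) that is unexpected" and related.

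**The concern.** A severity scale should not stop assigning grades as the value gets worse. In these three rows it does, whenever the value passes the Grade 3 limit and the fever or dialysis condition is absent.

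Because Section 11.11 leaves laboratory results out of its grade limb, Section 11.13 is the only mandatory, grade-based stop for an individual subject that reaches a laboratory value. A related value in the gap would not trigger it on a literal reading. It would also not count toward pausing criterion 4, and it would be missing from any table of laboratory AEs by grade, such as Table 4.

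The third vaccination has been given in all arms (Section 1.7), and no dose follows the fourth. What remains at stake is whether a subject with a related main-phase value in the gap may receive dose 4. Exclusion criteria 4 and 5 (Section 6.4) would not necessarily catch such a subject. They concern values at screening and allow inclusion at the investigator's discretion, so a value that has since resolved would pass.

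**Working it through.** No sample-size or power figure bears on this point. The check is to apply the rows as printed on both sides of each Grade 3 limit and then apply Section 11.13.

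**1. Grades as printed**

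| Row | Value | Side condition absent | Side condition present |
|---|---|---|---|
| WBC decrease | 1.0 | 3 | 3 |
| WBC decrease | 0.9, 0.5 | none | 4 |
| Creatinine, male | 177, 221.00 | 3 | 3 |
| Creatinine, male | 221.01, 300 | none | 4 |
| Creatinine, female | 160, 215.99 | 3 | 3 |
| Creatinine, female | 216.00 | none | none |
| Creatinine, female | 216.01, 300 | none | 4 |

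Female 216.00 falls between a Grade 3 band ending at 215.99 and a Grade 4 limit starting above 216.00.

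**2. The other laboratory rows.** Without any side condition, neutrophils of 0.4 and 0.1 are Grade 3. Male haemoglobin 6.4, female haemoglobin 5.9, platelets 24, ALT 601 and WBC increase 25.1 are all Grade 4. The gap is confined to the three rows above.

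**3. Whether other text supplies a grade**

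- Table 7 (Section 11.3.1) applies to AEs that are not in the Appendices; these parameters are.
- Footnote 1 to the laboratory table calls the values guidelines but gives no rule for a value past Grade 3.
- Footnote 2 can raise a value to Grade 4 because of associated signs or symptoms. It does not reach an asymptomatic value.

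**4. Effect on the stop.** For a related value in a man, 200 lies within 177.00–221.00, is Grade 3, and bars further vaccination. A value of 300 without dialysis has no grade, so the stop is not triggered.

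**5. Where the creatinine gap begins.** With the Appendix B reference limits (98 for men, 72 for women), it starts at 221/98 = 2.3 times the upper limit in men and 216/72 = 3.0 times in women. No other row covers it.

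**6. How far the neutrophil row covers the WBC gap.** Neutrophils cannot exceed the total count. At WBC 0.4 or lower they are therefore below 0.5, which is Grade 3. Above that, Grade 3 requires a neutrophil share below 0.5/WBC:

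- WBC 0.9: 0.5/0.9 = 55.6%
- WBC 0.8: 0.5/0.8 = 62.5%
- WBC 0.7: 0.5/0.7 = 71.4%

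If the share is higher, the neutrophil grade is only 1 or 2. In the least favourable case, with neutrophils equal to WBC, counts of 0.5–0.7 give Grade 2 and 0.8–0.9 give Grade 1.

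**7. Pausing criterion 4.** It needs 0.30 × 70 = 21 subjects in a vaccine arm, or 0.30 × 35 = 10.5, so 11, in a control arm. A rare value would seldom decide it.

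**8. Experience so far (Section 1.7.1).** 744 + 71 + 16 = 831 AEs are reported, all Grade 1 to 3, with two Grade 3 laboratory events and no Grade 4 AE. The affected parameters do move in this population. Grade 1 WBC decreases number 34 + 23 = 57 and Grade 1 creatinine increases 20 + 6 = 26, together 83 of 153 Grade 1 laboratory AEs (54%).

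**The case against.** The strongest reply is that the table is not meant to be read mechanically. Footnote 1 calls the values guidelines, and Section 11.3.1 has the investigator assess severity. A sensible investigator would call a creatinine of 300 at least Grade 3.

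Other routes also exist. Under Section 11.3 a clinically evident diagnosis replaces the laboratory finding as the AE. A renal diagnosis has no row in Appendix B, so Table 7 would apply, and its Grade 3 covers events needing medical evaluation or therapy. The value could be judged a medically important SAE; if related, a single case pauses the whole study under criterion 1 of Section 11.10. Criterion 6, investigator withdrawal, vaccination deferral, exclusion criteria 4, 5, 9 and 23, and the DSMB's review of main-phase data before the booster (Section 11.7) are further safeguards. To reach dose 4, a related gap value would have to be left ungraded, not diagnosed, not called serious, resolved or accepted at screening, and passed by both investigator and DSMB.

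This is right about the size of the problem, and it is why the effect is small. It does not close the gap. None of these provisions gives an asymptomatic value past Grade 3 a grade, and each depends on judgement or a further condition, whereas the Section 11.13 stop is mandatory.

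A second objection also stands: the count of 831 AEs is weak reassurance. An ungraded value might not appear in a summary organised by grade, so the absence of reported cases does not show that none occurred.

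**Conclusion.** The concern holds: the three rows are wrong as written. WBC below 1.0 without fever, male creatinine above 221.00 without dialysis, female creatinine above 216.00 without dialysis, and female creatinine of exactly 216.00 in any circumstances have no grade. Milder values in the same rows are Grade 3 and, if related, end dosing.

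The practical effect is small. Such values should be rare in healthy adults, the neutrophil row covers part of the WBC gap, and the discretionary safeguards are substantial. The conclusion rests on a literal reading of Appendix B and on the value being judged related to vaccination. Whether any stored main-phase value falls in the gap cannot be settled from the documents. The change should be made because the table feeds a mandatory safety rule and the correction is exact and nearly free.

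**What to change.** Amend the three rows so that Grade 3 applies to every value past its lower threshold unless Grade 4 is met:

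- WBC decrease: Grade 3 is below 1.5.
- Creatinine, male: Grade 3 is 177.00 or above.
- Creatinine, female: Grade 3 is 160.00 or above, and the Grade 4 limit becomes 216.00 or above.

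For the two creatinine rows, an alternative is to let either the value or the need for dialysis qualify for Grade 4, as the haemoglobin rows do with transfusion. Values past the limit would then be Grade 4 instead of Grade 3, and both trigger Section 11.13. That wording does not suit the WBC row, where fever alone would then be graded. The sponsor medical monitor should choose between the two.

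Before dose 4, check all stored main-phase WBC and creatinine values against the corrected rows, and apply Section 11.13 to any related value that becomes Grade 3 or higher.

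The cost is an edit to three rows of Appendix B and one database query. No new samples or visits are needed.

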4.4 Sample Size and Estimated Duration of the Study

A total of 210 volunteers will be enrolled/randomized in this trial, 70 subjects in each arm vaccine arms (Arm 1 and 2) and 35 subjects in each control arms (Arm 3a and 3b). A total of 140 subjects will receive PfSPZ Vaccine and 70 will only receive placebo.

Definitions for the purpose of this study:

- **Screened** – subjects will receive a study screening number when the informed consent is signed and will either be determined as “eligible” or “screen failure” as noted below.
 - Screening may be completed over the course of multiple visits.
 - Screening, in most cases, will occur within 56 days prior to administration of vaccine #1.
 - If the screening visit is >56 days administration of vaccine #, then an updated medical review and laboratory testing (CBC, ALT, Creatinine, ECG, Urinalysis, Pregnancy test (for females) will be completed to determine eligibility for enrollment.
 - **Note:** HIV, Hepatitis B, Hepatitis C and ECG are to be repeated during booster phase screening **ONLY IF** clinically indicated
- **Eligible** - subjects will be considered eligible to enroll once they have completed the screening procedures and have **met all inclusion** and **not met exclusion** criteria.
- **Screen Failure** – subjects are considered screen failures when they meet one of the following criteria after signing consent:
 - Screening results reveal that the subject is ineligible.
 - Subject withdraws consent before being vaccinated and/or randomized.
 - Subject cannot present to clinic for enrollment prior to study completing enrollment.
 - Subject is determined eligible for enrollment after study completes enrollment.
- **Randomized** – the subjects are considered randomized when they meet the following criteria:
 - Meet eligibility criteria.

- Study identification number (ID) assigned.
- Randomization number assigned.
- **Enrolled** – In the main phase, subject will be considered enrolled beginning with the collection of baseline labs on study Day -14.
 - In the booster phase, subject will be considered enrolled beginning with the receipt of artemether/lumefantrine prior to receiving 4th vaccination
 - Subjects enrolled in main phase but have not received the first vaccination may be replaced up to the accrual ceiling set for the study.
- **Discontinued/Withdrawn** – subjects are considered discontinued when they meet one or more of the following criteria:

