13 STATISTICAL CONSIDERATIONS

13.1 Endpoints and Statistical Methods

13.1.1 Safety analysis

Safety will be assessed by line listing and tables at the individual level. Intention-to-treat (ITT) group comparisons, between the vaccine arms and the control arm, will be performed in terms of the proportions of solicited AE, related AE and SAE. Other concerning trends will be investigated as needed or requested by the PI, ISM, IND sponsor, and/or DSMB.

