13.2 Sample Size Consideration

Sample size consideration is primarily based on VE evaluation. Seventy subjects will be enrolled in each arm. If the annual drop-out rate is between 15% and 28%, there will be 50 to 60 available subjects for efficacy evaluation at one year after study initiation. With 50 samples per arm, the study is capable of detecting the protective efficacy of vaccine with 88% power if VE is 45% and the background infection rate is 0.7 (see [Table 8](#)). With 60 samples per arm, the study has 83% power if VE is 45% and background infection rate is 0.6. For safety evaluation, with 70 subjects in each arm, there is 90% probability of observing at least one AE in the arm if the adverse event rate is no less than 0.033.

Based on data from existing studies, the number of participants in the booster phase will be close to that in the main phase. The above sample size consideration should approximately apply to the booster phase.

Table 8: Power for group-wise comparison based on logrank test on time to infection

Sample Size per Arm	Background Infection Rate	Vaccine Efficacy (VE)	Power
50	0.6	0.45	76
50	0.6	0.3	44
50	0.6	0.25	33
50	0.7	0.45	88
50	0.7	0.3	59
50	0.7	0.25	45
60	0.6	0.45	83
60	0.6	0.3	51
60	0.6	0.25	39
60	0.7	0.45	93
60	0.7	0.3	67
60	0.7	0.25	52
70	0.6	0.45	89
70	0.6	0.3	57
70	0.6	0.25	44
70	0.7	0.45	96
70	0.7	0.3	73
70	0.7	0.25	59

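### Laboratory safety is compared between arms only through graded events, and Appendix B leaves wide ungraded zones beyond its own printed limits, so a uniform 1.5-fold ALT shift would almost never be detected

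*Combined protocol and SAP*

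**What the plan says.** Section 13.1.1 sets out individual listings and tables, and then intention-to-treat comparisons that "will be performed in terms of the proportions of solicited AE, related AE and SAE". It names no test or significance level for these, and no analysis of laboratory values or of change from baseline. Table 6 in Section 11.3 lists haemoglobin, white cells, neutrophils, platelets, creatinine and ALT as solicited laboratory events. Section 11.3 takes the defining values from the toxicity table, which is in Appendix B. (One sentence there cites Appendix C, which is the reference list.)

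Appendix B grades ALT from 75.0 U/L and prints a normal limit of below 41. Creatinine Grade 1 is "107.00 – 132.99" µmol/L in women (printed limit 72) and "124.00 – 150.99" in men (printed limit 98). Platelets have one grading row for both sexes, with Grade 1 at 100-110, although the printed lower limits are 144 in women and 114 in men. A footnote calls the cut-offs guidelines that depend on institutional normals, and adds: "Institutional normal reference ranges should be provided to demonstrate that they are appropriate". The ranges printed come from Bancoumana adults; the trial site is Ouelessebougou.

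The only numerical safety-sensitivity statement is in Section 13.2: with 70 per arm, "there is 90% probability of observing at least one AE in the arm if the adverse event rate is no less than 0.033".

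**The concern.** Safety is the primary objective. A value beyond the printed limit but short of Grade 1 does not enter the between-arm comparison, unless an investigator chooses to report it as medically important under Section 11.3. Exclusion 5 in Section 6.4 keeps out most people whose ALT or creatinine is above the local limit. If the local limit is near 41, a post-dose ALT of 42-74 will usually be a new abnormality that carries no grade.

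ALT and platelets are reasonable analytes to watch here. The sporozoites invade hepatocytes (Section 1.3), and one Grade 3 platelet decrease in this trial was judged possibly vaccine-related (Section 1.7.1, still blinded). The risk is that a real but modest shift in a whole arm goes unseen, although the values that would show it are already being collected.

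**Working it through.** **1. The plan's own figure.** P(at least one event) = 1 − (1 − 0.033)^70 = 0.905, so the stated 90% reproduces. For a control arm of 35 it is 1 − (1 − 0.033)^35 = 0.69. This describes seeing one graded event. It says nothing about values that are never graded.

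**2. Grade 1 start against the printed limit (Appendix B).**

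| Row | Grade 1 starts | Printed limit | Ratio |
|---|---|---|---|
| ALT | 75 | 41 | 1.83 |
| Creatinine, women | 107 | 72 | 1.49 |
| Creatinine, men | 124 | 98 | 1.27 |
| White cells, increase | 11.5 | 9.0 | 1.28 |
| White cells, decrease | 3.3 | 3.6 | 0.92 |
| Neutrophils | 1.0 | 1.3 | 0.77 |
| Platelets, women | 110 | 144 | 0.76 |
| Platelets, men | 110 | 114 | 0.96 |
| Haemoglobin, women | 9.0 | 9.1 | 0.99 |
| Haemoglobin, men | 10.3 | 10.8 | 0.95 |

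ALT has the widest relative gap.

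**3. What the ALT gap costs.** The documents give no ALT distribution, so one is assumed: log-normal, 41 as the 97.5th percentile, log-SD s = 0.3, 0.4 or 0.5. The median is 41/exp(1.96s), which gives 22.8, 18.7 and 15.4 U/L. Every vaccinee's value is multiplied by m, with one post-dose draw and 70 v 35 subjects. The test is assumed to be Fisher's exact, two-sided 0.05. For a cut c, the share above it is 1 − Φ(ln[c/(median × m)]/s).

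Example, s = 0.4 and m = 1.5: the shifted median is 28.1. The share at or above 75 is 1 − Φ(2.46) = 0.7%, and the share above 41 is 1 − Φ(0.95) = 17%.

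For the log-value comparison, the standardised difference is ln(1.5)/s. At s = 0.5 it is 0.81, and the non-centrality is 0.81 × √(70 × 35/105) = 3.9, giving 97% power.

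| Uniform rise | Share ≥75 | Power, graded | Power, cut at 41 | Power, log ALT |
|---|---|---|---|---|
| 1.5-fold | 0.4-0.9% | about 0% | 31-94% | 97-100% |
| 2-fold | 3.7-4.8% | 0.4-2% | 96-100% | about 100% |
| 3-fold | 17-38% | 90-100% | about 100% | about 100% |

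The graded figures are low because, with no graded control, 8 of 70 vaccinees are needed for significance (8/70 v 0/35, p = 0.0497; 7/70 v 0/35, p = 0.092).

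**4. Repeated draws.** Take the worst grade over six draws with an assumed within-subject correlation of 0.7. Graded power stays at or below 0.2% for a sustained 1.5-fold rise (74-100% at 41). It rises to about 51-79% for a sustained doubling.

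**5. Platelets.** The printed ranges are taken as 2.5th-97.5th percentiles of a log-normal. For women the geometric mean is √(144 × 413) = 244 and the log-SD ln(413/144)/3.92 = 0.27. For men they are √(114 × 335) = 195 and ln(335/114)/3.92 = 0.27. Power at 70 v 35, one draw:

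| Uniform fall | Graded: men only | Graded: 50% women | Graded: women only | Sex-specific limit | Log platelets |
|---|---|---|---|---|---|
| 20% | 23% | 4% | <0.1% | 31-34% | 98% |
| 30% | 85% | 56% | 3% | 91-93% | about 100% |

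In men, moving the cut to the limit itself adds little (23% to 31% for a 20% fall). That loss comes from dichotomising a small sample. In women the cut-off is the main cause.

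**The case against.** The strongest objection is that uniform shifts favour a comparison of means. For marked rises in a minority, grading does as well as or better than a cut at the limit. If 15% of vaccinees have an 8-fold rise, graded power is 66-84%, against 56-58% above 41 and 62-85% on log ALT. With 15% at 5-fold the picture is mixed (graded 18-76%, above 41 49-58%). This stands, and it is why the grades should stay and the continuous analysis be an addition.

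A reader might infer four stronger things that the documents do not support.

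- **That earlier trials showed a vaccine effect on the liver.** Section 1.4.3.3.2 reports three Grade 3-4 transaminase cases in the randomised phase: 1 vaccine and 2 placebo, 14 to 65 days after ASAQ, with no significant laboratory difference between groups. The fourth case was in the uncontrolled pilot, also after ASAQ. The 2/46 v 0/47 ALT increases in Table 2 give Fisher p = 0.24.
- **That women are graded later throughout.** The haemoglobin row runs the other way. The sex mix of the trial is not given.
- **That the ALT row was built on a limit of 60.** The boundaries 75, 150, 300 and 600 form a doubling series. They fit 1.25, 2.5, 5 and 10 times 60, and equally 1.5, 3, 6 and 12 times 50.
- **That the footnote is breached.** It calls the cut-offs guidelines and asks for ranges, which are printed. It does not require Grade 1 to start at the limit.

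The cut-offs are the same in every arm, so they do not bias the comparison. The grades are not inert either: Section 1.7.1 reports 52 Grade 1 neutrophil decreases and 26 Grade 1 creatinine increases. Section 13.1.1 also allows concerning trends to be investigated, but that is not a pre-specified comparison.

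**Conclusion.** The point holds as a loss of sensitivity. The Appendix B ratios are exact and rest on no assumption, as does the absence of any planned analysis of laboratory values.

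The power figures depend on the assumed log-normal shape, a shift common to all vaccinees, one draw, Fisher's test at two-sided 0.05, and 70 v 35. On those terms grading misses a 1.5-fold ALT shift almost entirely, and repeated draws do not rescue it. It also misses a doubling on a single draw, though less so on worst grade over repeated draws. It finds a 3-fold shift.

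It would go too far to call the safety comparison blind to liver or platelet toxicity. Marked individual rises are graded, and in men the platelet cut-off costs little. The change is worth making because safety is the primary objective and the data already exist.

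**What to change.** Leave every Appendix B grade as it is. The grades feed pausing criterion 4 (Section 11.10) and the Grade 3 withdrawal rule (Section 11.13), and main-phase events have already been graded on them. Add to Section 13.1.1, for each regimen against its own control and for each phase:

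- a comparison of log ALT, creatinine, platelets and neutrophils as continuous post-dose values, adjusted for the pre-dose value, with 95% confidence intervals and with the draw (or the summary over draws) named in advance;
- descriptive counts of subjects outside the sex-specific limits that the local laboratory uses, since the printed ranges come from another community.

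Separately, the sponsor should reconcile the ALT, creatinine and platelet grading rows with the printed reference ranges. No cut-off is proposed here.

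The cost is analysis-plan wording and a few tables from safety bloods already scheduled in Appendix A. More low-level changes will be displayed, and some differences will arise by chance. Four analytes in two regimens make 8 comparisons per phase, so about 8 × 0.05 = 0.4 would be expected below 0.05 with no true effect. The results should therefore be presented as supportive estimates.
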